## 19.0 Risks to Subjects

*19.1 In your opinion, what is the overall risk (physical and nonphysical) to research subjects in this study (minimal, greater than minimal or unknown)*

minimal

*19.2 Describe if any subjects are withdrawn from therapeutic procedures or drugs (e.g., washout periods) prior to, or during, their participation in the study.*

N/A

*19.3 List the reasonably foreseeable risks, discomforts, hazards, or inconveniences to the subjects related to their participation in the research. Consider physical, psychological, social, legal, and economic risks. Include a description of the probability, magnitude, duration, and reversibility of the risks.*

*NOTE: Breach of confidentiality is always a risk for identifiable subject data.*

If a woman has been sedentary she may experience muscle soreness from participation in the exercise program that will dissipate after 4-7 days of regular exercise. In addition, a previously sedentary woman may experience initial fatigue (lasting 1 to 2 days) which will also dissipate within 4-6 weeks of consistent exercise. Participation in this research has minimal risks to the mother and fetus and all participants will be instructed as to what constitutes adverse responses and when to not engage in exercise. For mothers in the structured exercise group (EX), transportation to the IHP may be inconvenient and/or difficult. Following delivery, it may be more difficult for mothers to engage in the exercise program (HOMEX and EX) if they don't have childcare.

*19.4 Describe procedures performed to minimize the probability or magnitude of risks, including procedures being performed to monitor subjects for safety.*

All exercise performed by the EX, HOMEX, and UC groups will follow ACSM and ACOG guidelines for moderate-intensity. In addition, all women will wear a Polar Ignite watch that will alarm if their HR exceeds moderate level intensity. All women in the EX will be supervised during their exercise sessions. Women in the HOMEX group will be meet individually with either [name] or [name] to discuss safe exercise principles. They will be given written information on exercising in a moderate intensity range for both cardiovascular and resistance

exercise. In addition, they will be contacted twice per week to discuss their program and any questions about exercise. Lastly, their HR data will be downloaded and analyzed to confirm that they are exercising in a moderate intensity rate. Women in the UC group will be told to continue participating in whatever activity they are currently engaged. They will be given an activity log to record their activity and we will download their HR data.

All women will be told that during exercise they may experience adverse changes including: abnormal blood pressure; fainting; and disorders of heart rhythm that can be minimized by stopping their exercise and immediately informing their physician of any unusual symptoms. In addition, they will be told to maintain their exercise intensity at a moderate level (conversational level) throughout each and all exercise sessions.

At the beginning and throughout the study, participants will be reminded that their participation is voluntary and they can stop participating in the study at any time.

With the exception of the depression questionnaires, the information being asked of participants is not sensitive information—e.g. how is your sleep, activity, fatigue and QOL? Participant information is confidential, not shared, securely kept, and coded by number.

While we will not be analyzing the data (e.g. results of depression or other questionnaires) during the study to avoid compromising interactions (e.g. bias) with participants, study personnel will be speaking to participants in the HOMEEX and EX groups multiple times per week. Participants will be asked about their next OB/GYN appointment and if anything about their health status has changed (this helps to also insure that each participant is maintaining an active relationship with her OB provider). The physician approval form that provides a participant with clearance to participate in the study will include a statement that asks the physician to inform study personnel immediately if the participant develops any contraindication, relative or absolute, to participation in an exercise program (e.g. fetal growth restriction or gestational hypertensive disorder). Gestational diabetes mellitus (GDM) will be handled per individual participant's OB/GYN recommendations. If a participant develops an absolute contraindication to participation in the study, they will be removed from the study. If a participant experiences an adverse event, a new clearance must be provided by OB/GYN for the participant to return to the study. In the case of an emergency, participants will be advised to seek care at Upstate Community Hospital. If a participant needs NICU care, they will be advised to seek care at Crouse or St. Joseph's hospital.

Only full term infants (birth at 37+ weeks gestation) will go on to participate in the neonatal portion of the study. Infants participating in this portion of the study will undergo monthly height, weight, motor and cognitive assessments that pose minimal to no risk to the infant. In the

event, that an assessment uncovers unexpected information (e.g. loss of weight, significantly delayed motor development), participants will be advised to contact their pediatrician.

Participants will regularly be asked how they are feeling. If a participant expresses that she is feeling blue or is having depressive thoughts, study personnel will recommend that she contact her health provider. We will follow up each week to check the status of these symptoms and to make sure they have spoken with their health provider. Participants in the control group are also being contacted weekly, so relationships are being established, and the same process for experiencing undesirable thoughts or feelings would apply.

*19.5 If applicable, indicate which procedures may have risks to the subjects that are currently unforeseeable.*

n/a

*19.6 Indicate which research procedures, if any, may have risks to an embryo or fetus should the subject be or become pregnant.*

N/A

*19.7 If you responded to 19.6 that there are such risks, how will you minimize the risk of a pregnancy occurring during the course of the study? (Select all that apply)*

- Counseling on birth control and /or abstinence
- Pregnancy test during the study
- Pregnancy test prior to initiation of the study
- Other \_\_\_\_\_
- N/A

*19.8 If applicable, describe possible risks to others who are not subjects.*

n/a

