submaximal treadmill test to determine HRR for the two exercise groups and estimate VO2max using the Pollock equation which will be repeated at 3- and 6-months after birth to compare aerobic fitness levels.

All women will complete the following questionnaires at baseline (late 1st trimester), 25-26 weeks (late 2nd trimester), and 37-38 weeks (late 3rd trimester), and monthly through 6-months post-natal: MFI, SF-12 QOL; PSQLI; CES-D; EPDS; and the PPAQ. All questionnaires have been demonstrated to have good validity, reliability, and internal consistency and the CES-D and EPDS are similar to each other in regards to internal consistency and test-retest reliability.

Infants from mothers in all three groups will have their gross and fine motor, and cognitive development measured monthly (months 1-6) at home using the Bayley Scales of Motor Development, 4th edition. The Bayley 4 is a standardized, norm-referenced tool with subtest level scaled scores, domain level composite scores, percentile ranks, and developmental age equivalents. Infant height and weight will be measured monthly through 6-months of age.

Women assigned to EX will have all of their supervised pregnancy exercise sessions, questionnaires, and weight measured at the IHP. After delivery, women assigned to EX will resume their supervised IHP exercise program between 4-8 weeks (depending on delivery mode) when they are cleared for activity by their physician, complete exercise testing at 3- and 6-months and will have monthly home visits for infant testing through 6 months. HOMEEX and UC women will visit the IHP at baseline, 3 & 6-months post-delivery for exercise testing, questionnaires, and weight measurement. HOMEX and UC groups will receive home visits for: 2nd & 3rd trimester questionnaires and weight measurement and every month post-delivery for questionnaires, weight measurement and infant testing.

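### No action is stated for a high individual CES-D or EPDS score, so a woman who reports symptoms on the form but does not voice them is not picked up

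*Combined protocol and SAP*

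**What the plan says.** Section 11.0 has every woman complete CES-D and EPDS at baseline, at 25-26 weeks, and then at "37-38 weeks (late 3rd trimester), and monthly through 6-months post-natal: MFI, SF-12 QOL; PSQLI; CES-D; EPDS; and the PPAQ". For the home-exercise and control arms, "HOMEEX and UC women will visit the IHP at baseline, 3 & 6-months post-delivery for exercise testing, questionnaires, and weight measurement"; home visits cover the remaining time points.

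Section 19.4 treats these scales as special: "With the exception of the depression questionnaires, the information being asked of participants is not sensitive information". It adds that "Participant information is confidential, not shared, securely kept, and coded by number".

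On the results it says "we will not be analyzing the data (e.g. results of depression or other questionnaires) during the study to avoid compromising interactions" with participants, giving bias as the reason. The same sentence points to frequent conversations with women in the two exercise arms. The referral step comes later in 19.4: "If a participant expresses that she is feeling blue or is having depressive thoughts, study personnel will recommend that she contact her health provider". After that, "We will follow up each week to check the status of these symptoms and to make sure they have spoken with their health provider". Control women are contacted weekly, and "the same process for experiencing undesirable thoughts or feelings would apply".

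Three further provisions bear on the point:
- Section 19.4 has staff ask about changes in health status and the next OB/GYN appointment.
- Section 11.3 gives a woman her results at once if she asks, otherwise a summary at the end of her participation. She decides whether her physician sees them.
- Section 14.2 has her OB/GYN and emergency contact informed after an adverse event.

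**The concern.** The study repeatedly collects two depression scales from pregnant and postnatal women, then states that the results will not be looked at while they are taking part. The only stated way into referral is what a woman says to staff. If she answers the form candidly but not the conversation, the study holds the information and no stated step uses it. What is at stake is participant safety, not the validity of a comparison. The response step (advice, then weekly follow-up) is already written and funded; a score simply cannot start it.

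**Working it through.** The plan gives no figure to reproduce. The check is a count of occasions, a comparison of triggers, and a test of the stated reason.

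**1. Number of occasions.** Inputs: the schedule in section 11.0 and the maximum of 18 women, six per arm, in section 6.1.
- Time points per woman: 3 prenatal (baseline, 25-26 weeks, 37-38 weeks) + 6 monthly post-natal = 9.
- Whole study: 18 x 9 = 162 at most. Per arm: 6 x 9 = 54.
- Measurement runs from September 2020 to April 2022 in the section 11.1 timetable: 4 + 12 + 4 = 20 months. 162 / 20 = 8.1 occasions a month.

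**2. Is staff contact available when forms are completed?** For home-exercise and control women: institute visits at baseline, 3 and 6 months (3), home visits in the 2nd and 3rd trimesters (2), and home visits at months 1, 2, 4 and 5 (4). 3 + 2 + 4 = 9 of 9 in person. Supervised-exercise women complete questionnaires at the institute during pregnancy and have monthly home visits for infant testing after delivery. Contact is therefore not the problem.

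**3. What starts an action?**

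| Information | Action during the study | Where |
|---|---|---|
| Woman voices low mood | Advised to contact provider, weekly follow-up, all arms | 19.4 |
| Woman reports a change in health status | Staff ask; no mood-specific step | 19.4 |
| Adverse event | OB/GYN and emergency contact informed | 14.2 |
| Woman asks for her results | Results given; no staff action stated | 11.3 |
| Unexpected infant assessment finding | Mother advised to contact pediatrician | 19.4 |
| Heart-rate data, home-exercise arm | Downloaded and analyzed to confirm intensity | 11.0, 19.4 |
| High CES-D or EPDS score | None stated; no cut-off, scorer or scoring time | no section |

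The plan already acts on individual infant findings and reviews individual heart-rate data while the study runs. The mother's depression score is the exception.

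**4. Does the stated reason require the rule?** The aim is to keep results from colouring how staff deal with participants. That requires staff who train, coach or call a woman not to know her score. It does not require that nobody does. Group analysis can stay deferred either way.

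**The case against.** The strongest reply is that this is a reasoned choice with an active safeguard. Section 19.4 gives the rule, the reason and the compensating contact together. Staff do not wait for a woman to volunteer symptoms: they ask how she feels, whether her health has changed and when she next sees her OB/GYN. Women in both exercise arms are spoken to several times a week and controls are contacted weekly. This stands and makes the gap small. It does not close it, because every route still depends on what she chooses to say. For controls, section 11.0 also allows the weekly contact to be a text or email reminder.

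Four stronger readings are tempting and are not supported:
- A reader might infer that there is no mood safeguard. There is one, in all three arms.
- A reader might take the rule as a ban on scoring. The text speaks of analysis, and the on-request access in section 11.3 suggests that individual results can be produced mid-study, although it does not say whether questionnaires count as testing.
- A reader might hold section 14.2 to its form prompt, which mentions a counselor for a study that screens for depression. That is an illustration under an if-applicable heading. The scales here are outcome measures being piloted, and the prompt creates no requirement.
- A reader might want a number of missed women. That would need a rate of high scores and a rate of disclosure; the documents give neither, so any figure would only restate the assumptions.

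It is also fair to say that consent pages were removed and that Supplemental Form B and the physician approval form are not included. A score-based step could sit there. If it does, 19.4 need only refer to it.

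**Conclusion.** The point holds in a narrow form. Followed exactly, the visible plan has no response to a woman who reports depressive symptoms on CES-D or EPDS but does not voice them. This is the consequence of a stated rule, and the bias rationale does not demand it. The firm measure of size is exposure: at most 9 occasions per woman, 162 in all, assuming full enrolment and complete follow-up. How often a high score would go unvoiced cannot be estimated from the documents. The existing safeguards limit the risk in a pilot of at most 18 women that the protocol rates as minimal risk. The case for change is that the data are already collected, the response already exists, and connecting them costs little.

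**What to change.** Amend section 19.4 as follows.

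1. Limit the no-analysis rule to group summaries and outcome analysis.
2. Name an existing team member who already handles the forms at data entry, where possible not the woman's coach, to score both scales within a few days of collection.
3. Pre-set a cut-off for each scale, agreed by the investigators and the IRB. A score above the cut-off on either scale is enough.
4. When a score is high, the scorer re-links the code number to the woman and starts the step 19.4 already has: advice to contact her health provider, then weekly follow-up. This is identical in all arms. An investigator is available as clinical backup, and the score is not passed to staff who coach her.
5. Check that the scorer is on the registration form (14.3) and the access list (16.3).

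**Cost.** One protocol paragraph and, if needed, one access-list entry. At an assumed 5 to 10 minutes for both scales, scoring takes 162 x 5 = 810 minutes (13.5 hours) to 162 x 10 = 1,620 minutes (27 hours) over the study. Each flagged woman adds 4 x 10 = 40 to 12 x 10 = 120 minutes, assuming 4 to 12 weekly contacts of 10 minutes.

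**Downsides.** One team member will know individual scores. Blinding of coaches may be incomplete: by section 14.3 the same two people supervise training, call home-exercise women and make the home visits, with helpers also assisting in sessions. Section 16.1 lists three people for data entry, but their names are removed, so whether one of them does no coaching cannot be checked. Referral may slightly influence later depression scores, as the existing verbal referral already can.

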### **1.0 Objectives**

*1.1 Describe the purpose, specific aims, or objectives of this research. Specifically, explain why it is important to do the study.*

Historically, pregnant women were advised to refrain from exercise due to concerns of maternal and fetal risk such as preterm delivery, low infant birth rate and fetal stress. Despite current research that has demonstrated substantial benefits for maternal, fetal, and infant health, only 9-15% of pregnant women meet the current physical activity recommendations. In addition, pregnancy exercise research is confounded by a lack of randomized controlled trials (RCT) that include diversity in participant demographics, specifically inner city populations, and difficulty accurately quantifying weekly exercise volume. We propose a pilot RCT investigating two different approaches to exercise intervention across a spectrum of demographics that we believe will result in improved exercise adherence as well as in maternal and infant health outcomes.

*1.2 State the hypothesis to be tested, if applicable.*

*NOTE: A hypothesis is a specific, testable prediction about what you expect to happen in your study that corresponds with your above listed objectives.*

Specific Aim #1: To determine the feasibility of two types of exercise interventions (supervised & home exercise) in terms of design, implementation and adherence. Our working hypothesis is that both supervised and home exercise interventions will be implementable as designed in pregnant women as evidenced by recruitment, eligibility, retention, follow-up and exercise adherence from 1st trimester through 6-months post-natal at a 60% rate, but that adherence to the two types of exercise interventions will differ by demographic. A secondary exploratory hypothesis is that we will be able to successfully recruit and retain 50% of our pregnant women from the Syracuse Community Health Center (primarily women with lower resources).

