Specific Aim #2: To determine the appropriateness of the outcome measures proposed for the exercise intervention in detecting changes in maternal aerobic fitness, quality of life (QOL), fatigue, sleep quality, depression, and weight change throughout pregnancy and 6-months post-natal as measured by the Balke Ware submaximal test; SF-12 Generic Quality of Life (QOL); Multidimensional Fatigue Inventory (MFI); Pittsburgh Sleep Quality Index (PSQLI); Center for Epidemiologic Studies Depression Scale (CES-D); Edinburgh Postnatal Depression Scale (EPDS); and the Pregnancy Physical Activity Questionnaire (PPAQ). Our working hypothesis is that the above outcome measures will be able to detect changes in maternal outcome measures in both exercise groups.

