## **5.0 Data Management and Analysis**

*5.1 Describe the data analysis plan, including any statistical procedures. This section applies to both quantitative and qualitative analysis.*

Statistical analysis used to determine feasibility of the exercise intervention will include general descriptive statistics to assess recruitment, eligibility, retention, follow-up and exercise adherence. In addition, we will conduct a survey and interview of subjects related to acceptability to participate in EX and HOMEEX and discuss barriers to regular exercise which will be analyzed using descriptive statistics and a phenomenological approach. To determine the feasibility of maternal and infant outcomes, Kruskal-Wallis and Friedman's ANOVA will be used to investigate between group and within group differences. Relationships between variables will be analyzed using Spearman correlation coefficient. Because this is a feasibility study, the results will be used as preliminary data to apply for future funding and also will provide variable quantitative and qualitative data for validating interventions that can increase adherence to exercise guidelines during pregnancy in women with different ethnic and socioeconomic backgrounds.

*5.2 If applicable, provide a power analysis for the number of subjects to be included. If qualitative research, so state, and provide general justification for the total number of subjects proposed.*

*NOTE: This may not apply to certain types of studies, including chart/records reviews, survey studies, or observational studies. This question is asked to elicit whether the investigator has an adequate sample size to achieve the study objectives and justify a conclusion.*

This is a pilot project aimed to investigate feasibility of approach and appropriateness of maternal outcome measures. If the working hypotheses are supported, the next phase will be a large, randomized intervention study. Pilot data from this project can be utilized in the power analysis for the larger study.

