## 18.0 Withdrawal of Subjects

N/A: This study is not enrolling subjects. This section does not apply.

18.1 Describe anticipated circumstances under which subjects may be withdrawn from the research without their consent.

Failure to take part in scheduled visits without notification AND failure to respond to attempts at contact.

18.2 Describe any procedures for orderly termination.

NOTE: Examples may include return of study drug, exit interview with clinician. Include whether additional follow up is recommended for safety reasons for physical or emotional health.

n/a

18.3 Describe procedures that will be followed when subjects withdraw from the research, including retention of already collected data, and partial withdrawal from procedures with continued data collection, as applicable.

If a subject withdraws from the study, their data will be included in the study up to the point of withdrawal.

18.4 Describe what will happen to data already collected.

Data that has already been collected will be stored physically and electronically as stated previously.

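### Removing a woman "from the study" for an absolute contraindication, with no further non-exercise follow-up described, would lose her later Aim 2 data, and how she counts toward 60% retention is unstated

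*Combined protocol and SAP*

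**What the plan says.** **Removal.** Section 19.4 (Risks to Subjects) sets the rule: "If a participant develops an absolute contraindication to participation in the study, they will be removed from the study". It is limited neither to the exercise programme nor to an arm. The next sentence lets a woman return to the study after an adverse event, given new OB/GYN clearance. Gestational diabetes is left to the OB/GYN's recommendation. No removal is stated for relative contraindications.

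**Data after withdrawal.** Section 18.3 answers: "If a subject withdraws from the study, their data will be included in the study up to the point of withdrawal". The form's prompt there also asks about "partial withdrawal from procedures with continued data collection, as applicable", and the answer describes none. Section 18.2, on orderly termination, is marked not applicable. Section 18.1 asks for the circumstances of withdrawal without consent and lists only "Failure to take part in scheduled visits without notification AND failure to respond to attempts at contact".

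**Aims.** Aim 1 (section 1.2) judges feasibility by "recruitment, eligibility, retention, follow-up and exercise adherence from 1st trimester through 6-months post-natal at a 60% rate". Aim 2 concerns "detecting changes in maternal aerobic fitness, quality of life (QOL), fatigue, sleep quality, depression, and weight change throughout pregnancy and 6-months post-natal".

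**Schedule and analysis.** Section 11.0 has all women complete questionnaires at baseline, at 25-26 weeks, at 37-38 weeks, and monthly to 6 months after birth. The treadmill test is at baseline and at 3 and 6 months after birth. Section 5.1 plans descriptive statistics for feasibility. For the outcomes it says "Kruskal-Wallis and Friedman's ANOVA will be used to investigate between group and within group differences". It gives no missing-data rule.

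**The concern.** A woman who may no longer exercise can still fill in fatigue, sleep, depression and quality-of-life questionnaires and be weighed. If removal from the study is applied as worded, these data stop when she becomes medically ineligible. The cause of the missing data is then her health, which is plausibly related to the outcomes themselves. Aim 2 asks whether the measures pick up change through to 6 months after birth, and section 2.1 asks this of all three groups. It would be answered in women selected for having stayed free of absolute contraindications.

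The rule also reaches the control group, whose only assigned study exercise is the treadmill test.

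For Aim 1, retention and follow-up are among the things the pilot exists to measure. Without a counting rule, the same events can be reported as meeting or missing 60%. Section 5 says that the pilot data will support funding applications and can feed the power analysis of the larger trial, so the ambiguity would carry forward.

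**Working it through.** The plan has no power calculation, dropout allowance or removal rate, so there is no figure of its own to reproduce. Its counts agree: 3 groups x 6 = 18 enrolled, and 18 x 3 = 54 screened (section 6).

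**1. Does any passage provide follow-up after removal?** Sections 11.0, 18.1-18.4 and 19.4 were set side by side. None does. Section 19.4 removes the woman, 18.3 keeps what was collected before, and 11.0 describes visits only for women still taking part.

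**2. Data lost per removed woman.** Questionnaire time points: 3 (baseline, 25-26 weeks, 37-38 weeks) + 6 (postnatal months 1-6) = 9.

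| Removed | Collected | Lost |
|---|---|---|
| After baseline, before 25 weeks | 1 | 8 of 9 |
| After 26 weeks, before 37 weeks | 2 | 7 of 9 |
| After 38 weeks, before postnatal month 1 | 3 | 6 of 9 |

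The later weights go with them. One woman is 1/6 = 16.7% of an arm and 1/18 = 5.6% of the trial.

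**3. How likely is a removal?** The rate p is an assumption. With independent women, P(at least one of 18) = 1 - (1 - p)^18.

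| Assumed p | Expected removals, 18p | P(at least one) |
|---|---|---|
| 1% | 0.18 | 17% |
| 2% | 0.36 | 30% |
| 5% | 0.9 | 60% |
| 10% | 1.8 | 85% |
| 15% | 2.7 | 95% |

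**4. Effect of the counting rule.** This step uses the group size and the 60% rate from the documents. The event counts are chosen to illustrate. Take an arm of six with one medical removal and two voluntary dropouts:

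- the removal counts as lost: 3/6 = 50%;
- she leaves the denominator: 3/5 = 60%;
- she stays in follow-up: 4/6 = 66.7%.

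**5. Could removals alone breach 60%?** If the rate is read per arm, 0.6 x 6 = 3.6, so four women must be retained and three losses breach it. P(at least 3 of 6) is 0.2% at p = 5%, 1.6% at 10% and 4.7% at 15%. Removals alone therefore rarely do so.

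**6. Together with other dropout.** Assume other dropout of 20%, so that total loss = 1 - 0.8(1 - p). P(at least 3 of 6) is 9.9% at p = 0, 10.9% at 1%, 12.0% at 2%, 15.4% at 5% and 29.4% at 15%. The p = 0 figure stands for perfect continued follow-up of removed women, which is the best case for the fix.

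**The case against.** The strongest reply is that the study may be loose wording for the exercise programme. The next sentence of 19.4 requires OB/GYN clearance to return to the study, and clearance in sections 7.1 and 9.1 is clearance to exercise. Section 18.3 answers for a woman who withdraws, and its prompt applies only where applicable, so its silence does not forbid continued questionnaires. This stands as far as it goes: a settled decision to discard data is not shown. But no passage provides for the follow-up either, and staff who apply the words literally would stop it.

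Other points stand in part:

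- A reader might infer that all women who become ill are lost. The documents do not support that. Only absolute contraindications lead to removal, and a return route exists after adverse events. The examples in 19.4 (fetal growth restriction, gestational hypertensive disorder) are given for contraindications, relative or absolute, so neither is shown to trigger removal.
- A reader might infer loss that differs by arm, since staff speak to the exercise groups several times a week and to controls weekly. But physician reporting covers every arm, and the documents do not say which conditions are absolute. Differential loss is not shown.
- Enrolment is limited to low-risk singleton pregnancies, so low removal rates are credible. At 1% to 2%, the effect on an arm's chance of missing 60% is small.
- Section 1.2 does not say whether 60% applies per arm or pooled. The per-arm figures are one reading.
- Friedman's test in its standard form drops any woman with a missing time point. That follows from the lack of a missing-data rule and is not specific to removals.
- The mismatch between 18.1 and 19.4 is largely editorial.

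**Conclusion.** The point holds in a limited form. As worded, 19.4 and 18.3 together end all data collection on a woman with an absolute contraindication, although questionnaires and weights need no exercise. Up to 8 of 9 questionnaire time points would go, for a health-related reason. Whether this is intended is unclear, and the passages must be reconciled.

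The frequency is unknown. The 17% to 95% chance of at least one removal rests on an assumed rate of 1% to 15% and independence between women.

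The gap in the counting rule does not depend on that rate. One removal and two dropouts in six can read as 50%, 60% or 66.7%. A reader might infer that removals would by themselves sink the feasibility criterion, but the calculation does not support this.

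This is an inexpensive improvement worth making before enrolment, because data not collected after removal cannot be recovered. It is not a flaw that defeats an 18-woman pilot.

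**What to change.** Leave the clinical rule on stopping exercise and exercise testing unchanged. Then:

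- In 18.3 and 19.4, define removal for data purposes as removal from exercise and exercise testing. State that the woman is invited to continue the planned questionnaires, weights and, where the infant is eligible, infant visits, unless she withdraws consent. Reconcile 18.1 with this.
- Analyse her in her randomised arm and keep her in the retention and follow-up denominators.
- Report medical removals by arm, separately from voluntary dropout, and treadmill tests not done as missing for a medical reason.
- Report adherence two ways: over all randomised women, and up to the medical stop. A woman barred from exercise cannot adhere, so a single figure would mix two things.
- For EX women, allow the two prenatal contacts at home, and add questionnaires and weight to the monthly postnatal home visits already planned for infant testing.

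**Cost.** Changes to protocol and consent wording, and an ethics amendment. At most 8 contacts per removed woman (2 prenatal, 6 postnatal), all already planned. At the $10 per face-to-face visit in section 23.1 that is at most 8 x $10 = $80, plus any reimbursed transport and staff time. Some women may decline, so the fix reduces the loss but does not guarantee complete data.
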